### 4.3 Screening Visit

Subjects that have not been treated previously with the PKG (i.e. PKG naïve) will be identified from routine clinical care, offered study participation, and provided a study informed consent document. Study goals and expectations will be discussed with subjects and all subject questions will be answered by a study Investigator and/or delegated designee. Subjects willing to participate will provide written informed consent.

Subject selection criteria will be documented. A Montreal Cognitive Assessment (MoCA) will be performed as part of selection criteria at the screening visit to exclude patients with dementia who are unlikely to be able to use the PKG independently. Only versions 7 or 8 of the MoCA will be used. Version and subform will be recorded in the screening visit CRF. Subjects who do not meet the study selection criteria will be documented as a screen failure on Subject Enrollment Logs in the Site Regulatory Binder and in the Electronic Data Capture system (EDC), as required. Eligible subjects will be assigned a Subject ID number and randomized using the EDC system in a 1:1 ratio to the PKG- Group (standard of care clinical assessments without use of PKG data) or the PKG+ Group (standard of care clinical assessments plus use of PKG data). Medical history and demographics will be collected on all patients after randomized into the study. The point of

enrollment into this study is when all selection criteria are met, an informed consent form is completed, and the randomization assignment has been completed.

A PKG Watch will be ordered through the GKC Portal and dispensed to the all subjects as previously described.

Screening and enrollment activities may be done remotely by phone or secure video conferencing (per existing site practices), as part of a routine clinic visit, as per local clinic and/or IRB requirements.

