### 5.3 Ancillary Endpoints

Ancillary endpoints will include measurements as indicated below:

- Rate of protocol defined adverse events affecting health care utilization including: hospitalizations, emergency department, urgent care or unanticipated clinic visits from baseline to 4 months, 1, 2, 3 years follow-up
- Rate of protocol defined adverse events and potential contraindications for increasing dopaminergic therapy including: falls, orthostatic hypotension, bothersome hallucinations, delirium, and impairment that prohibits interaction with the PKG watch from baseline to 4 months, 1, 2 3 years follow up
- Rate of enrolled subjects in PKG + group who are unable to be brought into Target Range through follow-up visits

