Statistical Analysis Plan

Utilization of Target Ranges to Treat Patients with Parkinson's Disease by Objective Measurement Using the Personal KinetiGraph® (PKG®) compared to Standard of Care Assessment (TARGET-PD)- A Randomized Controlled Trial

Global Kinetics Corporation

Effective Date: 09Sep20

Version: 1.0

Approved By:

Printed Name/Title

[name]
Director Clinical Research
Global Kinetics

Signature

A handwritten signature in black ink, appearing to read "[name]", written over a horizontal line.

Date

14Sep20

[name]
Biostatistician
Director, Product Development Strategy, NAMSA

[name]

Digitally signed by [name]
DN: cn=[name], o=NAMSA,
ou=C&C,
email=[contact],
c=US
Date: 2020.09.14 13:44:32 -05'00'

Table of Contents

1. Introduction	3
2. Abbreviations	3
3. Study Objectives	3
3.1. Primary Objective	3
3.2. Hypothesis	4
3.3. Primary Endpoint	Error! Bookmark not defined.
3.4. Secondary Objective	5
3.5. Secondary Endpoints	5
3.6. Ancillary Endpoints	9
4. Study Design	10
4.1. Sample Size	10
4.2. Randomization	10
4.3. Blinding	11
4.4. Study Assessments and Missing Data	11
4.5. Analysis Populations	11
4.6. Interim Analyses	Error! Bookmark not defined.
5. Methods	12
5.1. General Considerations	12
5.1.1. Descriptive Statistics	12
5.2. P-Values	12
6. References	12
7. Appendix 1 - LED Calculation	14
8. Appendix 2 – Statistical Tables	16

1.Introduction

The purpose of this statistical analysis plan is to describe the methods that will be used to analyze and report the clinical utility of Personal KinetiGraph movement recording system data in the clinical management of Parkinson’s disease (PD) using objective measurement and target ranges in neurology and movement disorders clinics in the U.S.

Subsequent versions of this analysis plan will document and describe any such changes. This plan is based on the protocol Version 1.0, dated June 6, 2019.

Prior to the planned protocol interim analysis, Global Kinetics notified all sites that enrollment was closed as of February 27, 2020. The contexts of this analysis plan will therefore reflect an adapted plan for all subjects enrolled prior to the notification of enrollment closure followed through the primary endpoint.

2.Abbreviations

- BKS: Bradykinesia Scores
- CGI-I: Clinician Global Impression of Improvement
- DKS: Dyskinesia Scores
- HCU: Healthcare resource utilization
- MDS: Movement Disorder Specialists
- PD: Parkinson’s Disease

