3.4. Secondary Endpoints

The following secondary clinical outcomes will be measured at and compared between baseline and 4 months follow-up visits.

Secondary clinical outcomes will include:

- 1. Percent “responders” for MDS-UPDRS Total score (based on a minimum clinically important change of >4 points)**

This is a comparison of the percent responders for the within-group change from baseline to 4 months for PKG+ and PKG- groups. This is a comparison of the percent responders for the within-subject change from baseline to 4 months for PKG+ and PKG- groups.

2. Change in motor endpoints from baseline to 4 months including:

a. MDS-UPDRS Part III

- i. Within-subject changes will be calculated as visit value minus baseline value such that a negative change reflects an improvement and positive change signifies a deterioration. Summaries of improved/same/worsened will be provided along with the continuous summaries. (example, 35 (4-month) – 45 (BL))

b. PKG Bradykinesia score (BKS),

- i. Within-subject changes will be calculated as visit value minus baseline value such that a negative change reflects an improvement and positive change signifies a deterioration. Summaries of improved/same/worsened will be provided along with the continuous summaries. (example, 25 (4-month) – 30 (BL))

c. PKG Dyskinesia score (DKS) and measurement of OFF time

- i. Within-subject changes will be calculated as visit value minus baseline value such that a negative change reflects an improvement and positive change signifies a deterioration. Summaries of improved/same/worsened will be provided along with the continuous summaries. (example, 5 (4-month) – 9 (BL))
- ii. Measurement of OFF time will not be included in this analysis

3. Change in PDQ-39 from baseline to 4 months

Change in PDQ-39 from baseline to 4-months. Tabulate values and proportions and changes from baseline to each visit.

Within-subject changes will be calculated as visit value minus baseline value such that a negative change reflects an improvement and positive change signifies a deterioration. Summaries of improved/same/worsened will be provided along with the continuous summaries.

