3.5. Ancillary Endpoints

Ancillary endpoints will include measurements as indicated below:

- Rate of protocol defined adverse events affecting health care utilization including: hospitalizations, emergency department, urgent care or unanticipated clinic visits from at 4 months
- Rate of protocol defined adverse events and potential contraindications for increasing dopaminergic therapy including: falls, orthostatic hypotension, bothersome hallucinations, delirium, and impairment that prohibits interaction with the PKG watch at 4 months
- Rate of uncontrolled subjects in PKG+ group who are unable to be brought into Target Range through follow-up visits ($BKS \leq 25$ or $DKS \leq 9$). This will also be run for a threshold of a PKG score of $BKS \leq 26$ at 4-months.

4. Study Design

This is a prospective, multi-center, single-blind randomized (1:1) controlled, longitudinal follow-up study (1, 2, 3 years).

This is a randomized controlled trial (RCT) to evaluate treating uncontrolled patients with Parkinson's Disease (PwP) to a target range established by a published expert opinion manuscript. The study aims to evaluate clinical patient outcomes, quality of life measures and health care utilization of those patients specifically treated to a target range when using the PKG data in the clinical management of Parkinson's disease (PD) in routine clinical care (treatment group) compared to those managed with medical history and clinical evaluation alone (control group) performed by a neurologist experienced in PD management. Both groups will be recommended to undergo medication changes until they reach a "controlled state" that is determined by either the clinician using standard of care (SOC) (PKG- Group) or using PKG based targets and SOC assessments (PKG+ Group). For subjects in the treatment arm (PKG+ Group) the references will be according to the following table for purposes of analysis using PKG scores*:

	Target Range
Bradykinesia Score (BKS)	Median BKS 23-25
Dyskinesia Score (DKS)	Median DKS 7-9

The main objective of this study is to evaluate whether PwP who are managed with the aid of objective measurement and use of target ranges have improved PD symptoms and outcomes as compared to individuals treated using only standard of care (medical history, neurological examination).

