4.4. Study Assessments and Missing Data

In the event inaccurate and/or incomplete PKG data collection occurs (e.g., subject wore PKG successfully but for less than the required duration, subject PKG Watch was not sufficiently secured creating PKG artifacts precluding interpretation, subject performed activities, such as the use of power tools, for a sufficient duration that interfered with PKG data collection, data collection completed when subject was OFF), data collection may be repeated one time. A note will be made in the case report form (CRF) that documents the reason for the repeated data collection and the initial and final test results will be recorded in the medical record. Only the final results will be recorded on the CRF and used for analysis purposes. Techniques will not be used to impute missing data; evaluable data will be utilized.

Due to the impact of COVID-19 on ability to collect select data, notations have been made in the protocol deviation section of the data extract and will be provided as a summary categorization for analysis purposes.

Specifically, for the MDS-UPDRS Part III data was either:

- Completely collected for baseline and/or 4-months visit
- Partially collected for baseline and/or 4 months visit (i.e., rigidity (Q 3.3) and postural stability (Q3.12) questions not collected if a telehealth visit)
- Not collected for baseline and/or 4-month visit

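### The SAP took effect after the last in-window 4-month visit and departs from the protocol without giving reasons; its BKS ≤26 run also mixes two cuts

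*SAP*

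**What the plan says.** The SAP title page gives "Effective Date: 09Sep20", and the signature dates are 14 September 2020. SAP section 1 states that "Global Kinetics notified all sites that enrollment was closed as of February 27, 2020" and that the plan is adapted for that reason. Protocol 4.3 sets the point of enrolment at the moment when selection criteria are met, consent is complete and "the randomization assignment has been completed". Section 4.4 of the SAP refers to an extract in which "notations have been made in the protocol deviation section of the data extract", and describes in the past tense whether MDS-UPDRS Part III was collected fully, partly or not at all.

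On the ancillary rate, Protocol 5.3 has "Rate of enrolled subjects in PKG + group who are unable to be brought into Target Range". SAP 3.5 restricts this to uncontrolled PKG+ subjects, with cuts of BKS ≤25 or DKS ≤9, and adds: "This will also be run for a threshold of a PKG score of" BKS ≤26 at 4 months. SAP 3.1 classes a subject as bradykinetic at BKS above 25.

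OFF time is a secondary endpoint in Protocol 5.2. In SAP 3.4, item 2c reads: "Measurement of OFF time will not be included in this analysis". No reason follows.

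**The concern.** A SAP finalised after the visits it analyses has to let the reader tell which choices came from the protocol and which were made late. This one does not. Its general text speaks of planned analyses throughout, and it marks none of its additions as exploratory or post hoc.

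The blinding provisions do not settle the matter. SAP 4.3 blinds subjects to assignment, and blinds PKG- subjects and staff to PKG scores. No blinding of the sponsor or the statistician is stated. SAP 4.2 has the statistician create the assignments, and Protocol 4.2 has the sponsor receive and process the watches of both arms. With 41 subjects, an open subgroup list and no multiplicity procedure, what can be concluded from the added analyses depends on when, and with what knowledge, they were chosen.

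The BKS ≤26 run has a further fault that does not depend on timing. It can count a subject as brought into range when the subject's score has not moved.

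**Working it through.** **1. Timing.** Inputs: enrolment closed on 27 February 2020 (SAP 1); baseline is 28 ± 7 days after screening, so at most 35 days (Protocol 4.4); the 4-month visit is 120 ± 30 days after baseline, so at most 150 days (Protocol 4.6). Randomisation takes place at screening.

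- Latest in-window visit: 27 Feb 2020 + 35 days = 2 Apr 2020; + 150 days = 30 Aug 2020.
- Gap to the effective date (9 Sep): 10 days. Gap to signature (14 Sep): 15 days.
- Reading 4 months as 122 calendar days: 35 + 122 + 30 = 187 days, giving 1 Sep 2020, still 8 days before the effective date.
- Nominal windows: 28 + 120 = 148 days, giving 24 Jul 2020.

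**2. Departures from the protocol.**

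| Item | Protocol | SAP | Explained by closure? |
|---|---|---|---|
| BKS ≤26 cut | absent; range is 23-25 | added (3.5) | no |
| Ancillary denominator | enrolled PKG+ (5.3) | uncontrolled PKG+ (3.5) | no |
| OFF time | secondary (5.2) | dropped (3.4) | no |
| Covariate-adjusted regression | detail deferred to the SAP (6.4) | absent | no |
| FDS in target range | FDS >7.5 and FDS <13 appear (4.4) | BKS and DKS only (3.1, 4) | no |
| Subgroups | no such list | seven bullets, list left open (3.2) | no |
| 1-3 year endpoints | secondary (5.2) | dropped | yes |
| mITT population | requires the 3-year visit (6.3) | dropped | yes |

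The SAP also adds a category for LED changes under 100 mg (3.4). The partial Part III analysis (3.2) is new too, but the SAP gives COVID-19 as its reason.

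**3. Entry and exit cuts in the BKS ≤26 run.** A bradykinetic subject enters at BKS >25 and succeeds at BKS ≤26. Anyone with 25 < baseline BKS ≤ 26 and no change is a success. The share is P(BKS ≤26 given BKS >25). The documents give no BKS distribution, so the range below is assumed:

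- Excess over 25 uniform on 0 to 10: 1/10 = 10%.
- Excess exponential with mean m: 1 − exp(−1/m). For m = 10, 9.5%; for m = 5, 18%; for m = 3, 28%.

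**4. Open subgroup list.** For scale only: seven independent tests at 5% with no true effect give 1 − 0.95^7 = 30% chance of at least one false positive. The last two bullets are two levels of one factor; counted as one, 1 − 0.95^6 = 26%. Independence is an assumption, since the subgroups share subjects.

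**The case against.** The strongest reply is that finalising a SAP after the last visit is not a defect in itself; what matters is access to outcomes by arm, and on that the documents are silent. The passage in SAP 4.4 concerns protocol deviations and whether Part III was collected. It mentions neither scores nor arms. Effective and signature dates are not decision dates, and the LED appendix is dated 28 January 2020, before closure. The SAP still describes follow-up of the 41 subjects in the future tense, and COVID disrupted visits, so the date of the last actual visit is unknown. All of this stands.

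The primary endpoint, two-sample t-test, one-sided 0.025 level and ITT population in SAP 3.2 match Protocol 6.1 and 6.3. The BKS ≤26 run is supplementary, concerns one arm only, and cannot bias the treatment comparison. That also stands.

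The denominator change has a sensible rationale, because a subject already in range cannot be brought into it. It also tends to work against the sponsor. For illustration with assumed counts, 8 failures are 8/20 = 40% of all enrolled PKG+ subjects but 8/16 = 50% if 4 were in range at baseline. What remains is that the change is not disclosed.

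The SAP does call itself adapted and states the OFF-time omission openly, and the protocol's schedule of events lists no separate OFF-time assessment. But the only reason given for adapting is enrolment closure, which explains none of the six items. The reply does not touch the mismatch of cuts.

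**Conclusion.** Two things hold. First, the SAP took effect 10 days after the last in-window 4-month visit and was signed 15 days after it, with an extract already in existence. It makes six departures from the protocol that closure does not explain, and it neither gives reasons for them nor says what had been seen when they were decided. The dates assume that nobody was randomised after 27 February 2020 and that visits stayed in window.

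Second, the BKS ≤26 run uses different cuts at entry and exit, so its rate is wrong as defined. The size of the error is unknown; 10% to 28% of bradykinetic subjects is only what the assumed distributions give.

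A reader might infer that the choices were made with results by arm in view, that all data collection had ended, or that the primary comparison is compromised. The documents support none of these. They show the collection status of Part III, a derived last in-window date, and a primary analysis carried over from the protocol. This is a fault of disclosure and labelling, plus one faulty supplementary rate.

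**What to change.** 1. For the supplementary run in SAP 3.5, use the same cut at both ends (denominator: PKG+ subjects with baseline BKS >26) or delete the run.
2. In SAP section 1, list every departure from the protocol with its reason, including the missing adjusted regression and the target-range definition without FDS, which must be reconciled with the protocol's table. State when the extract was taken and what data by arm had been seen when each departure was decided.
3. Class the added cuts and subgroups as exploratory, and as post hoc if outcomes by arm had been seen. Delete the wording in SAP 3.2 that leaves the subgroup list open.
4. Report the protocol's rate among all enrolled PKG+ subjects beside the rate among uncontrolled subjects.

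The cost is SAP wording and one extra table row. Some analyses lose pre-specified status.

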4.5. Analysis Populations

The primary analysis will be based on the intent-to-treat (ITT) population defined as all randomized subjects analyzed according to the treatment group assigned.

In addition, analyses based on the per-protocol (PP) population will be performed for the primary and secondary endpoints. The PP population is defined as all subjects who are randomized and adhere to the study protocol requirements, including: meeting all of the subject selection criteria, completion of the PKG Watch wear period, inability for investigator to further make treatment changes due to known contraindication, completion of subject surveys and completion of follow-up visits.

Subject selection criteria can be found in the study protocol.

5. Methods

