#### 3.2 Exclusion Criteria

**Subject with any of the following clinical criteria should be excluded:**

- Contraindication to increasing levodopa (e.g. orthostatic hypotension, hallucinations/psychosis or any other medical condition in the last year that would preclude increasing levodopa or other appropriate Parkinson's Disease medications)
- MoCA score <23 at screening visit
- Diagnosis of Essential Tremor
- Wheelchair bound or bedridden
- Currently utilizing or planning in the next 6 months advanced PD therapies (DBS, infusion, etc.)
- In the investigator's or sponsor's opinion, subject has any unstable or clinically significant condition that would impair the participant's ability to comply with study

requirements or interfere with interpretation of the study endpoints (e.g., subject unable to complete PKG watch wear instructions per Patient Instruction Manual)

Subjects will be assessed in the ON state where applicable.

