#### *Parkinson's Disease Medication Use*

All subjects in the study will be asked to continue taking Parkinson's disease medication(s) as prescribed by their Parkinson's clinician throughout the duration of this study. Any modifications to medicines made during this study will be based on the clinician's judgment. Changes to medications will be recommended until the patient is considered to be controlled

unless contraindications are identified by the investigator. All PD medications and subsequent changes will be recorded in the medication log CRF. In addition, non-PD prescription medications of anti-depressants, anti-psychotics and blood pressure lowering agents will be tracked in the other medication log CRF.

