#### 4.5 Interim Follow-Up Visits

Interim follow-ups will be completed for subjects who are not considered to be controlled. For PKG- group subjects, controlled means per clinician standard of care assessment and for PKG+ group subjects, this is per the Acceptable Target Range:

	Target Range
Bradykinesia Score (BKS)	Median BKS 23-25 and/or FDS > 7.5
Dyskinesia Score (DKS)	Median DKS 7-9 and FDS < 13

Interim visits can be completed in-clinic or remotely via telephone per institutional requirements. This timeframe may vary depending on a variety of factors such as physician care practices, amount of total medication change needed, subject medication regimen compliance and subject tolerance to medication changes.

Approximately 28 days prior to each planned subject follow-up visit, a PKG Watch will be ordered through the GKC Portal and dispensed to each subject as previously described and PKG report obtained prior to the visit of PKG+ group subjects for investigator review.

For subjects in the PKG+ Group, the site staff will ensure the PKG is available prior to the Interim Follow-up Visit. Protocol required data collection will occur at each follow-up interim visit. A Subject "ON" State Assessment will be completed and changes in medical history and medications will be recorded. Any protocol defined AEs that have occurred will be captured on the AE Reporting CRF (see Section 8). The study investigator will review the PKG provided by GKC prior to the visit and use the information to guide the discussion with the subject during the clinical assessment. PKG results will be recorded in the PKG Reporting CRF. The study investigator will complete the Clinician Assessment CRF to denote patient-reported symptoms, treatable findings, and clinical management planning based on his/her routine clinical assessment procedures along with the PKG information.

For subjects in the PKG- Group, protocol required data collection will occur at each follow-up interim visit. A Subject "ON" State Assessment will be completed and changes in medical history and medications will be recorded. The study investigator will complete the Clinician Assessment CRF to denote patient-reported symptoms, treatable findings, and clinical management planning based on his/her routine clinical assessment procedures. The study investigator will be blinded to the PKG information during interim visits.

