These steps will be repeated for each interim follow-up until the study subject is determined to be controlled or a maximum of the 4-month follow-up visit.

Up to 4 medication changes including at the Baseline visit and up to 3 interim visits will be allowed to get each subject into a “controlled” state. Interim follow-up visits end when PD symptoms have become optimized (considered controlled on oral therapies) per standard of care assessments for PKG- group subjects and per the Acceptable Target Range as published in Pahwa et al., 2018 and no further treatment changes are indicated as assessed by the study investigator and the subject will proceed to the next required study visit at 4-months Follow-Up.

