**Table 1. Schedule of Events**

Study Activity	Screening	Baseline (28 days; +/- 7 days)	Interims (Up to 3 visits)	Follow-Up (4 month +/- 30 days)	Annual follow-ups (1, 2, 3 year +/-2 months)
Visit Type	In-clinic or phone per standard of care	In-clinic 21-35 days	In-clinic or phone per standard of care	In-clinic 90-150 days	In-clinic
Medical History	X				

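### The per-protocol definition (SAP 4.5) lists a contraindication to further treatment changes as a requirement for membership, where an exception was evidently meant (minor)

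*SAP*

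**What the plan says.** SAP 4.5 makes ITT the primary population and adds PP analyses of the primary and secondary endpoints. It defines PP as randomized subjects who adhere to the protocol's requirements, then lists five of them: the selection criteria, the PKG Watch wear period, "inability for investigator to further make treatment changes due to known contraindication", the subject surveys and the follow-up visits. The items stand in parallel. No connecting word marks the third as an exception or an exclusion. Protocol 6.3 has the same wording, so the protocol does not correct the SAP.

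Contraindications also appear in three other places:

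- Protocol 3.2 begins its exclusion criteria with "Contraindication to increasing levodopa".
- Protocol 4.2, on PD medication use, recommends medication changes until the subject is controlled, "unless contraindications are identified by the investigator".
- SAP 3.4, under change in PKG scores, plans a rate of subjects who needed a treatment change but could not have one because of a contraindication, and remarks that this group may show no effect on outcomes.

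**The concern.** Four of the five items are things an adherent subject does or satisfies. The third describes a circumstance that most adherent subjects should never meet. Read as a requirement like its neighbours, it reverses the purpose of the set: a subject who is eligible, wears the watch, completes the surveys, attends the visits and has no contraindication fails PP.

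What is at stake is the supportive analysis. The protocol's modified ITT set, which required the 3-year visit, was not carried into the SAP, so PP is the only population besides ITT in which the primary and secondary endpoints are to be analysed. A programmer who codes the list as written gets the wrong set. One who sees the problem has to supply a rule that the plan does not state.

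**Working it through.** The plan gives no PP size, so there is no figure to reproduce. The check is a logical reading of the definition, followed by simple counts.

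**Step 1: the literal rule.** Membership is the conjunction of the five items. A subject who meets the other four enters PP only if the third is also true, that is, only if a known contraindication prevented further changes.

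**Step 2: interaction with eligibility.** The first item requires all selection criteria to be met, and protocol 3.2 excludes a contraindication to increasing levodopa or other appropriate PD medications at entry. The first and third items therefore pull against each other. The literal set would hold mainly subjects whose contraindication arose or became known after screening.

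**Step 3: consistency with conduct.** Under protocol 4.2 the recommendation to change medication lapses when the investigator identifies a contraindication. A subject whose changes stop for that reason has departed from nothing, and so satisfies the lead-in to the PP definition, which is adherence. SAP 3.4 treats such subjects as a subgroup to be counted, which makes no sense if every PP member must belong to it.

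**Step 4: counts under three readings.** Inputs:

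- N = 41 enrolled subjects (SAP 4.1). This is an upper bound on the number otherwise adherent.
- c = share of otherwise adherent subjects with such a contraindication. The documents do not give it; 0% to 30% is an assumed range, for illustration only.

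Formulas: literal requirement = N × c; exception (subject stays in) = N; exclusion (subject is taken out) = N × (1 − c).

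| c (assumed) | Literal | Exception | Exclusion |
|---|---|---|---|
| 0% | 41 × 0 = 0 | 41 | 41 |
| 10% | 41 × 0.10 = 4.1 | 41 | 41 × 0.90 = 36.9 |
| 20% | 41 × 0.20 = 8.2 | 41 | 41 × 0.80 = 32.8 |
| 30% | 41 × 0.30 = 12.3 | 41 | 41 × 0.70 = 28.7 |

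The literal set is the exact complement of the exclusion set: N × c + N × (1 − c) = N. If the sponsor meant to exclude these subjects, the clause as written selects precisely the wrong ones. The two sensible readings coincide when c = 0 and differ by N × c subjects otherwise. Because of the entry criterion in step 2, the lower rows of the table are the less likely ones.

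**The case against.** The strongest reply is that nobody would apply the clause literally. A rule that returns a nearly empty set would be noticed the first time it was run, and the documents already point to its meaning: the adherence lead-in in SAP 4.5 and the exception in protocol 4.2 together favour keeping these subjects. On that view all that is missing is a connecting word. Much of this stands. It is why the point is minor, and why the exception reading is the natural default. It does not make the definition usable, because the stated rule is wrong and not merely short of detail. The remark in SAP 3.4 that this group may show no effect on outcomes could also be taken as a motive for leaving such subjects out.

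A reader might infer more than the documents support:

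- **That the two sensible readings are equally open.** They are not. Protocol 4.2 favours the exception.
- **That the rule would be chosen with outcomes in view.** By the protocol's windows, a subject screened on the enrolment closing date of 27 February 2020 had baseline due by 2 April (35 days) and the 4-month visit due by 30 August (150 days more), 10 days before the SAP's effective date of 9 September 2020. This assumes visits within window, while SAP 4.4 reports COVID-19 disruption to data collection. Nothing shows that the PP set had been derived or that outcomes by arm had been seen.
- **That the last items, "completion of subject surveys and completion of follow-up visits", oblige subjects to complete the annual visits.** The SAP Introduction limits the plan to "all subjects enrolled prior to the notification of enrollment closure followed through the primary endpoint", so the analysis ends at month 4.
- **That PP carries all the supportive weight.** SAP 3.2 also plans a COVID-19 analysis and subgroup analyses of the primary endpoint. The modified ITT set that was dropped required the 3-year visit and could not have served a 4-month analysis.

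**Conclusion.** The PP definition in SAP 4.5 and protocol 6.3 is wrong as written. It turns a permitted reason for stopping medication changes into a condition of membership, and so drops every adherent subject without a contraindication. The error is plainly one of drafting.

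Its reach is limited to the supportive PP analyses of the primary and secondary endpoints. The ITT primary analysis does not depend on it. The actual size cannot be stated, since it turns on a count that the documents do not give; the table above rests on an assumed share and on all 41 subjects being otherwise adherent. No direction of bias can be stated for either sensible reading. Severity: minor.

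**What to change.** In SAP 4.5, take the clause out of the list of PP requirements and restate it as an exception: a subject whose further medication changes stopped because of a documented contraindication still counts as adherent. If the sponsor meant to leave such subjects out of PP, the SAP should say so explicitly as an exclusion. Settle the choice before the PP set is derived and without reference to outcomes by arm, and note in the SAP that the definition differs from protocol 6.3.

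The cost is one or two sentences in the SAP and no protocol amendment. The sponsor should also check that the case report forms identify these subjects. The rate planned in SAP 3.4 covers those contraindicated to a needed change, but does not expressly cover those who stopped after an earlier change.
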